Trial Participants	Postmenopausal women with osteopenia or osteoporosis	
Planned Sample Size	120 (max 165)	
Treatment duration	6 months	
Planned Trial Period	26 months	
	Objectives	Outcome Measures
Primary	Decrease in bone resorption	Urine NTX
Secondary	Increased selenium Decrease in bone turnover Increase in physical functioning Increased antioxidant activity Decreased inflammatory markers	Serum Se, SePP Serum CTX, PINP, osteocalcin SPPB score, grip strength Glutathione peroxidase, hydroperoxidase IL-6, hsCRP
Investigational Medicinal Product(s)	Selenase (Biosyn, Germany) Sodium selenite pentahydrate	
Dose	200mcg daily, 50mcg daily, placebo	
Route of Administration	Oral	

TRIAL FLOW CHART

LIST OF ABBREVIATIONS

AE	Adverse Event
AR	Adverse Reaction
AUBM	Academic Unit of Bone Metabolism, Sheffield
BMD	Bone Mineral Density
CRF	Case Report Form
CRF	Clinical Research Facility
CTA	Clinical Trial Authorisation
CTIMP	Clinical Trial of Investigational Medicinal Product
CTX	C-terminal cross-linking telopeptide of type I collagen
DMEC	Data Monitoring Committee
DSUR	Development Safety Update Report
DXA	Dual Energy X-ray Absorptiometry
EudraCT	European Clinical Trials Database
GCP	Good Clinical Practice
GMP	Good Manufacturing Practice
HbA1c	Glycated haemoglobin
HRA	Health Research Authority
HRT	Hormone Replacement Therapy
hsCRP	highly sensitive C-Reactive Protein
HTA	Human Tissue Act
IB	Investigator Brochure
ICH	International Conference on Harmonisation of technical requirements for registration of pharmaceuticals for human use.
IL-6	Interleukin-6
IMP	Investigational Medicinal Product
IMPD	Investigational Medicinal Product Dossier
ISF	Investigator Site File
ITT	Intention to Treat
MHRA	Medicines and Healthcare products Regulatory Agency
NHS R&D	National Health Service Research & Development

NIHR	National Institute for Health Research
NTX	N-terminal cross-linking telopeptide of type I collagen
OC	Osteocalcin
PINP	Procollagen type I N propeptide
PI	Principal Investigator
PIC	Participant Identification Centre
PIS	Participant Information Sheet
PPI	Patient and Public Involvement
QA	Quality Assurance
QC	Quality Control
RCT	Randomised Control Trial
REC	Research Ethics Committee
RSI	Reference Safety Information
SAE	Serious Adverse Event
SAR	Serious Adverse Reaction
SePP	Selenoprotein P
SERM	Selective Estrogen Receptor Modulator
SOP	Standard Operating Procedure
SmPC	Summary of Product Characteristics
SPPB	Short Physical Performance Battery
STH	Sheffield Teaching Hospitals
SUSAR	Suspected Unexpected Serious Adverse Reaction
TMG	Trial Management Group
TSH	Thyroid Stimulating Hormone
TSC	Trial Steering Committee

1. RESEARCH QUESTION

Does selenium supplementation decrease bone turnover or improve muscle function in postmenopausal women with osteopenia or osteoporosis?

2. LAY SUMMARY

This research aims to determine whether selenium supplements improve bone and muscle health in older women at risk of osteoporosis (low bone density or weak bones) and fracture (broken bones).

Osteoporosis is a major public health problem. One in two women and one in five men over age 50 will have a fracture. Fractures cause pain, disability and reduce life-expectancy. Women with below-average bone density around the time of the menopause might have previously taken hormone replacement (HRT) to prevent osteoporosis, but HRT is much less used now due to side effects. Therefore there is a need for safe, effective and inexpensive preventative interventions for women at risk of osteoporosis.

Selenium is a chemical nutrient present in several human proteins, including anti-oxidants. Anti-oxidants may protect against ageing of tissues, including bone, by mopping up damaging reactive oxygen molecules (sometimes called 'free radicals'). Selenium is present in soil, and so is obtained from many foods. However, soil selenium levels are low in Europe, and dietary intake in the UK is below recommended levels.

We previously found that women with higher blood selenium levels have stronger bones, but this doesn't prove that giving selenium will improve bone strength.

We propose a randomised controlled trial to compare selenium supplements with a placebo (dummy treatment) in women with below-average bone density. We will give selenium (at two different doses) or placebo to 120 women for six months and use blood and urine tests and bone density scans to see if giving selenium does have any effect on bone. We will also do muscle function tests and measurements of free radical molecules.

3. BACKGROUND

One in two women and one in five men over the age of fifty will have a fragility fracture. Fractures lead to pain, disability, loss of independence and increased mortality. This is a huge health burden for affected individuals, the NHS and social care which is increasing as the population ages.

About 30% of women aged over 65 are osteopenic (below-average bone density), and at risk of developing osteoporosis and fractures. More than 50% of all fractures in postmenopausal women occur in women with osteopenia. These women are not eligible for osteoporosis treatment at present because of the individual risk/benefit ratio and economic factors. Previously, these women could have been offered hormone replacement therapy (HRT) for bone protection, but adverse effects of HRT have limited its use.

Therefore there is a need for an effective, safe, well-tolerated, inexpensive and widely applicable preventative option for osteopenic women.

Selenium is a chemical element present in several human proteins. Twenty-five human selenoproteins have been identified (1). Known functions of selenoproteins include thyroid hormone synthesis (iodothyronine deiodinases) and antioxidants (thioredoxin reductases and glutathione

peroxidases) (2, 3). Selenoproteins are anti-inflammatory and antioxidant; they reduce interleukin-6 and reactive oxygen species both of which are potent stimuli for bone resorption (4-6).

Selenium is obtained from the diet and it is rich in seafood, meat and cereals. The main determinant of food selenium content is soil selenium content. The recommended adequate intake for adults aged over 50 in the UK is 75ug/d for men and 60ug/d for women (7), but in the UK, the mean intake is only 40mcg/day (8). Selenium intakes have been declining in the UK in the past few decades, and are generally low in Europe compared with the USA. The main reason for the decreasing intake in the UK is a change in the source of flour for bread-making from North America (which contains higher selenium) to Europe due to economic and consumer demands. More recently, the levels of selenium in UK soils have declined as a result of changes in fertiliser practice (e.g. replacing single superphosphate with triple superphosphate) and reduced industrial emissions.

We recently reported that in 1144 older women from the UK, France and Germany, higher serum selenium or selenoprotein P was associated with higher bone mineral density of the lumbar spine and total hip, and lower biochemical markers of bone turnover (9). High bone turnover is the principal mechanism of osteoporotic bone loss. We also noted associations of selenium levels with balance, grip strength and pulse rate. Others have reported an association of selenium with muscle strength (10), but we were the first to explore bone turnover or bone density. Selenium status was inversely related to thyroid hormone status (selenium is required for thyroid hormone synthesis), but the associations of selenium with bone measures were independent of thyroid hormones.

It is plausible that selenium would affect bone metabolism. Selenoproteins are found in osteoblasts and osteoclasts (11). Selenoproteins are anti-inflammatory and reduce interleukin-6, a potent stimulus for bone resorption (5). Selenoproteins are anti-oxidant and reduce reactive oxygen species; these also stimulate bone resorption via increased RANK-L signalling (11). An increase in reactive oxygen species has been proposed as a key mechanism by which sex hormone deficiency causes age-related bone loss through the same RANK pathway (12). Therefore is possible that selenium could directly antagonise the cellular mechanism of postmenopausal osteoporosis.

There is experimental animal evidence to support the hypothesis that selenium has a role in bone and reduces bone turnover. Selenium deficient mice have poorer bone microarchitecture, higher bone resorption markers and higher inflammatory markers than selenium supplemented mice (13). Selenium deficient rats have poor bone microarchitecture and abnormal skeletal growth (14, 15).

There may also be an epidemiological association between selenium deficiency and bone health. In a study of US hip fracture risk in women over age 65 years, the counties with highest rates were in a belt across the south of the USA and the lowest rates were in the north (16). In contrast, a current map of soil selenium content in the USA shows the highest selenium content in the north of the USA and the lowest in a belt across the south of the USA
(<http://mrdata.usgs.gov/geochem/doc/averages/se/usa.html>).

Endemic selenium deficiency in humans has been associated with the osteoarthropathy Kashin-Beck disease (17).

Several other age-related disorders are linked to inadequate selenium status, including poor cognitive function (4) and selenium may be an independent predictor of mortality among older community-dwelling adults (18).

The possible adverse effects of selenium supplementation are thyroid dysfunction (because some selenoproteins are involved in thyroid hormone synthesis) and increased risk of type 2 diabetes mellitus (although in a previous study at the same dose and duration of treatment as this protocol there was no increase in diabetes (19)).

4. RATIONALE FOR CURRENT STUDY

If selenium supplementation were effective in reducing bone turnover and increasing BMD, this would offer an affordable, low risk prevention strategy that could be attractive to patients because it is a nutritional supplement, rather than a 'medicine'.

This study will give clear evidence of efficacy, and if positive, will identify the likely effective dose.

If this study is positive, we will immediately apply for funding to take the best dose (the lowest dose with a clinically significant clinical effect on bone turnover) into a longer study with bone density as the primary endpoint.

5. HYPOTHESIS AND OBJECTIVES

Hypothesis: Selenium supplementation decreases bone turnover in postmenopausal women with low bone density by reducing pro-resorptive reactive oxygen species.

Purpose: to determine if selenium supplementation is beneficial for osteoporosis prevention and muscle function in postmenopausal women.

Objectives: to determine if six months selenium supplementation in postmenopausal women with osteopenia or osteoporosis

- decreases bone turnover
- increases bone density
- improves physical function score and grip strength
- is safe (particularly for thyroid function and diabetes)
- is well-tolerated
- decreases markers of oxidative stress and inflammation

All of these objectives will be answered at the completion of the study and analysis, with a total project duration of 26 months.

6. RESEARCH DESIGN SUMMARY

This is a double-blind, randomised, placebo controlled trial.

We will evaluate two doses of selenium (50 and 200mcg daily) vs placebo over six months.

Participants are postmenopausal women with osteopenia or osteoporosis (T-score -1.0 to -3.0).

We will include participants with any baseline serum selenium concentration for generalisability, but the primary endpoint efficacy analysis will only include women with baseline serum selenium below 120mcg/l.

Primary endpoint: Urinary N-telopeptide of type I collagen (NTX/Cr).

Secondary endpoints: other bone turnover markers, BMD, muscle function, thyroid function, blood glucose, anti-oxidant activity, inflammatory markers

We will make the primary analysis based on women with baseline serum selenium below 120mcg/l. To ensure adequate power for this analysis we will plan to recruit 120 women (we expect that 100 of the 120 will have serum selenium below 120 mcg/l based on our previous cross-sectional study). We will review the baseline serum selenium results when 40 women have been recruited to confirm the expected distribution of baseline levels, and we will adjust the total recruitment number accordingly to ensure at least 99 women with serum selenium below 120mcg/l have been randomised for the final primary endpoint intention-to-treat analysis.

Participants will be randomised according to a schedule produced by Sharp Clinical Services.

Randomisation will be carried out independently of the study investigators. The blind will only be broken if judged by the PI as clinically necessary for the wellbeing of a participant.

If at the interim analysis, less than 60% of women recruited have serum selenium below 120 mcg/l the study recruitment strategy will be reviewed and discussed with the funder to determine if the trial should proceed.

The study may be stopped early if the investigators, sponsor or DMEC identify a safety concern.

Trial management will be done by the Academic Unit of Bone Metabolism CTIMP group (who meet monthly), and progress reported to the AUBM management group and Lay Panel. We will establish a TSC and DMEC.

7. STUDY POPULATION

Participants will be recruited from an existing volunteer database, patients attending the Sheffield Metabolic Bone Centre, mailing from GP surgeries and email and poster adverts.

7.1 Inclusion criteria

- Women
- Aged over 55, and at least 5 years since last menstrual period.
- Osteopenia or osteoporosis (DXA BMD lowest T-score between -1.0 and -3.0 at lumbar spine or total hip), who do not require pharmacological treatment for fracture prevention
- Willing and able to give informed consent

7.2 Exclusions

- Diabetes mellitus
- Thyroid dysfunction (history of hyper- or hypothyroidism, or TSH outside the STH reference range)
- any conditions known to affect bone metabolism
 - inflammatory disease (inflammatory arthritis, inflammatory bowel disease)
 - parathyroid disease
 - malabsorption (coeliac disease, pancreatic exocrine insufficiency)
 - alcohol intake >21 units per week

- prolonged immobility (in bed or using a wheelchair for more than three months within the last five years)
 - fracture in the last year
 - major orthopaedic surgery in the last year
- Taken selenium supplements in the last 60 days (women who are taking selenium supplements but want to participate in the trial will be offered the option to stop their supplement and have a 60 day washout before screening).
- Previous adverse reaction to selenium or any of the IMP or placebo excipients
- Current or recent medications known to affect bone metabolism
 - Bisphosphonates (12m before)
 - Teriparatide (12m before)
 - Denosumab (12m before)
 - Oestrogen or any sex steroids (12m before)
 - Aromatase inhibitors (12m before)
 - Tamoxifen or raloxifene (12m before)
 - Active vitamin D metabolites; calcitriol, 1 α -calcidiol (6m before)
 - Anti-epileptics; phenytoin, carbamazepine, primidone, valproate (6m before). Low dose use for migraine or neuralgia is not an exclusion.
 - Oral, IM or IV glucocorticoids (6m before)
- Women taking calcium and vitamin D supplements will not be excluded as long as they have been taking the calcium and vitamin D for at least 60 days and are planning to continue throughout the trial.

7.3 Bone density definitions

Normal bone density is defined as T-score above -1.0.

Women with normal bone density are not eligible to enter the study.

Osteopenia is defined as T-score -1.0 to -2.5.

Most women with osteopenia do not receive treatment with bisphosphates or other medication because their fracture risk is not high enough to justify the cost and exposure to side-effects. These women will be eligible to enter the study.

Some women with osteopenia (T-score -1.0 to -2.5) do require pharmacological treatment because factors other than BMD indicate a high risk of further fracture (eg prevalent vertebral fracture). These women will not be eligible to enter the study.

Osteoporosis is defined as T-score below -2.5.

Treatment with bisphosphonates or other medication is advised for most women with osteoporosis. These women will not be eligible to enter the study.

Some women with osteoporosis do not require pharmacological treatment because factors other than BMD indicate that they are not yet at high risk of fracture (eg relatively young age with no previous fractures, no other risk factors). These women will be eligible to enter the study.

Some women with osteoporosis are recommended to receive treatment with bisphosphonates or other medication, but decide not to take treatment (eg because of concerns about side-effects). These women will be eligible to enter the study.

Patients recruited through the Metabolic Bone Centre will have already have had BMD measurement with fracture risk assessment and a treatment recommendation from a Metabolic Bone Centre doctor.

Potential participants (from GP mailing and adverts) who have not previously had BMD and fracture risk assessment will have BMD and fracture risk assessment at screening. The PI (who is also a Metabolic Bone Centre doctor) will make the assessment according the same criteria as patients attending the Metabolic Bone Centre. If the potential participant is at high risk of fracture and requires treatment they will be excluded from the study and the PI will write to the patient and their GP with treatment advice.

7.4 Generalisability

We will measure baseline serum selenium levels to explore the relationship between baseline selenium levels and response to supplementation, but we will not exclude participants based on their serum levels. By having an unselected group can we explore whether there is a subset that should be targeted or whether everyone benefits. If selenium supplementation proves to be an effective preventative measure for women with osteopenia, a requirement for baseline selenium measurement might impede widespread adoption, and potential implementation as a public health measure.

To ensure all participants are vitamin D replete, they will be given a single oral dose of 100,000IU colecalciferol at the screening visit (NIMP).

8. PLANNED INTERVENTIONS

The intervention is a medicinal product containing sodium selenite. We will study two doses: 50 and 200mcg daily. The preparation is sodium selenite tablets 'Selenase' 50mcg and 200mcg (Biosyn, Germany). The tablets will be overencapsulated and a matching placebo will be manufactured to maintain the blind.

The mean difference between selenium levels in a replete population (USA) and the UK is about 60mcg/L. The mean increase in serum selenium with 200mcg/day is 90 mcg/L (19). 200mcg/day is a clinically effective dose in Graves' ophthalmopathy. Therefore 200mcg will be enough to achieve repletion in the majority of subjects and to determine whether selenium repletion has a clinically significant effect on bone turnover. If we see no effect at this dose we will be confident to accept the null hypothesis.

The 50mcg dose will assess whether a lower dose might be effective for musculoskeletal health – if its effect on bone turnover is similar to the 200mcg dose we could recommend the 50mcg dose for clinical use, at lower cost and lower risk of adverse effects.

This is a short, low risk study of a medication that we expect to be well tolerated. We are very experienced in recruiting and retaining patients in clinical trials. We expect compliance to be good and loss to follow-up to be low (less than 10%). We will make telephone contact with participants between study visits (every month) to maintain their engagement and check for adverse effects.

The required minimum sample size for the primary endpoint is 21 per group. We will recruit 33 per group into the primary analysis to allow for drop-out, group imbalance and secondary endpoint analysis.

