13. STATISTICS

13.1 Power calculation

A 20% (10nmol BCE/mmolCr) decrease in urine NTX is a plausible and clinically significant effect size.

In a previous study, 200mcg daily for six months increased serum selenium by 90mcg/L (19).

In our observational study of serum selenium and bone turnover markers, the regression coefficient of serum selenium and NTX/Cr was -0.101 (9), so if the relationship were causative we would expect an increase in serum selenium of 90mcg/L to be associated with a reduction in urine NTX/Cr of 9 nmol BCE/mmolCr (approximately 20%).

In support of this estimate, we would not expect as large a change in bone turnover as would be seen with a potent anti-resorptive drug such as a bisphosphonate (about 60%), but it might be

similar to a weaker anti-resorptive such as a SERM. In a study of six months' treatment with the SERM lasofoxifene (37), NTX decreased by 29%. We have also used this study as a model for the likely SD (12.5) and the correlation between NTX/Cr at baseline and six months (0.7).

A 20% decrease in NTX is clinically significant; a 20% decrease in NTX (about 1 standard deviation decrease) with bisphosphonate treatment is associated with a 30% decrease in incident vertebral fracture (38).

To achieve 90% power to detect this mean difference at the 2.5% (two-sided) level will require 21 patients per group. To allow for dropout, group imbalance and the secondary endpoint analyses we will recruit 33 patients per group with serum selenium below 120mcg/l (99 patients in total).

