17. RANDOMISATION

Participants will be block randomised equally to the three treatment arms.

The randomisation list will be generated by Sharp Clinical Services. The list will be supplied to STH pharmacy and a copy retained by Sharp.

At randomisation, participants will be allocated a study ID number which corresponds to their randomised medication number (the ID number will be in the format SE???, where ??? is the randomised medication pack number).

The code list will be stored in STH pharmacy, in a sealed signed envelope under the supervision of the study pharmacist, or out-of-hours duty pharmacist. This envelope is signed when opened and resealed for audit purposes. If emergency access is required out of hours, the PI or if unavailable, another metabolic bone consultant can be contacted through STH switchboard. If they agree that the code need to be broken, the duty pharmacist will access the list.

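### A null result at 200 mcg can rule out an effect of about the design size (20%), but the design does not support accepting the null hypothesis, as section 8 intends

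*Protocol*

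**What the plan says.** Section 8 argues that 200 mcg daily is enough to make most participants selenium replete, and so to show whether repletion has a clinically significant effect on bone turnover. It then concludes: "If we see no effect at this dose we will be confident to accept the null hypothesis". What would count as seeing no effect is not defined there or elsewhere in the protocol.

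Section 13.1 sets the effect of interest: "A 20% (10nmol BCE/mmolCr) decrease in urine NTX is a plausible and clinically significant effect size". It also derives the reduction expected at 200 mcg, 9 nmol BCE/mmolCr, from the regression coefficient in the group's observational study. On sample size it states: "To achieve 90% power to detect this mean difference at the 2.5% (two-sided) level will require 21 patients per group". The number is raised to 33 per group in the primary analysis population to cover dropout, group imbalance and the secondary endpoints. Section 8 expects loss to follow-up below 10%.

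Section 13.2 compares six-month NTX/Cr between groups by ANCOVA adjusted for baseline and applies the Hochberg procedure. It gives no margin, no equivalence test and no rule for interpreting a non-significant comparison.

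**The concern.** A superiority test can fail to reject the null hypothesis, but it cannot establish it. High power for a large effect justifies saying that the large effect is unlikely. It does not justify saying that there is no effect.

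The most natural reading of seeing no effect is that the 200 mcg comparison is not significant, since section 13.2 offers no other criterion. On that reading the protocol commits the investigators in advance to a conclusion that the data may not support. On any other reading the statement has no defined meaning. In both cases, a real but moderate reduction in bone resorption could be reported as absent.

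**Working it through.** **Inputs (section 13.1 unless stated).** SD 12.5; baseline to six-month correlation 0.7; target 10 nmol, called 20%, so the implied mean is 10 / 0.20 = 50; expected effect 0.101 × 90 = 9.09, stated as 9 nmol (9 / 50 = 18%); two-sided level 2.5%; power 90%; 33 per group planned. Loss below 10% (section 8) gives at worst about 33 × 0.9 = 29.7, or 30 per group. Allocation is equal across three arms (section 17).

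**1. The protocol's own figure.** ANCOVA residual SD = 12.5 × √(1 − 0.7²) = 8.93. Normal approximation: n = 2 × (2.241 + 1.282)² × 8.93² / 10² = 19.8, so 20 per group. With the t distribution it is 21 (error df from three arms) or 22 (two arms). The stated 21 reproduces, with a target of 10 nmol.

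**2. Precision at the planned size.** SE = 8.93 × √(2/n). The half-width of the 97.5% interval is t(0.9875; 3n − 4) × SE, which is also the smallest significant estimate.

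| n per arm | SE | Half-width | Power, 5 nmol | Power, 9 nmol | Power, 10 nmol |
|---|---|---|---|---|---|
| 33 | 2.20 | 2.277 × 2.198 = 5.01 | 0.50 | 0.964 | 0.988 |
| 30 | 2.30 | 2.281 × 2.305 = 5.26 | 0.46 | 0.946 | 0.979 |

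**3. What a null result excludes.** An estimate of zero at 33 per arm gives about −5.0 to +5.0 nmol (at 30, −5.3 to +5.3). Both 9 and 10 nmol are excluded. A reduction of up to about 5 nmol, 10% of the implied mean of 50, is not.

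**4. When a null result is still compatible with 9 nmol.** The estimate must lie above 9 minus the half-width and yet be non-significant:

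- 33 per arm: from 9 − 5.01 = 3.99 up to 5.01.
- 30 per arm: from 9 − 5.26 = 3.74 up to 5.26.

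If 9 nmol is the true effect, a result of this kind occurs in about 2% of trials at 33 per arm and about 4% at 30.

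**5. Effect of Hochberg.** When the 200 mcg P-value is the larger of the two, it is judged at 5%. At 33 per arm the 95% half-width is 4.36, so a borderline non-significant result has its limit at 2 × 4.36 = 8.73 (unrounded inputs), below 9. At 30 per arm the limit is 9.16. Power for 5 nmol at this more favourable level is 0.615 (n = 33) or 0.573 (n = 30). A true 10% reduction would still be missed in roughly 40% of trials.

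**6. Sensitivity (assumption, not a protocol figure).** If the correlation were 0.5, the 97.5% half-width at 30 per arm would be 6.38 and power for 9 nmol 0.82. With no gain from baseline adjustment, these become 7.36 and 0.69.

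**The case against.** The best defence is that the sentence is part of a dose justification. It says that 200 mcg achieves repletion, so a null finding could not be blamed on too low a dose. The question just before it concerns a clinically significant effect, and the only effect the protocol calls clinically significant is 20%. For that effect the trial is well powered, and power of 50% for half the design effect is ordinary. The statistics section contains no acceptance rule, and detailed interpretation may be left to the SAP.

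Much of this stands. It lowers the severity, and it means that the 5 nmol figures do not show a faulty sample size. But the sentence speaks of the null hypothesis, not of excluding 20%, and nothing in section 13 narrows it.

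A reader might infer something stronger: that any non-significant result at 200 mcg would be compatible with the 9 nmol the protocol expects. The figures do not support this. At 30 to 33 per arm it is true only for estimates close to the significance boundary, and at 33 per arm with Hochberg's 5% level not even there. Repeating the calculation at 21 per arm would make the problem look larger, but going from 33 to 21 is a 36% loss, against the under 10% that section 8 expects. Nor does the protocol say that the programme stops after a null result; section 4 states only what follows a positive one.

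**Conclusion.** The concern holds in a limited form. As planned, a null result at 200 mcg with an estimate near zero would credibly rule out a 9 to 10 nmol (about 20%) reduction. It would not rule out reductions of up to about 5 nmol (10%), and a true effect of that size would be missed in about half of trials at the 2.5% level (50% at 33 per arm, 54% at 30). Accepting the null hypothesis therefore goes beyond what the design can show.

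This rests on SD 12.5, correlation 0.7, an untransformed analysis and 30 to 33 evaluable women per arm. A lower correlation or a larger SD would widen the intervals and strengthen the point. Whether a 10% reduction matters clinically is not settled by the protocol, and the conclusion does not depend on it. Severity is modest: the sentence is in the dose rationale, and no sample size or test needs to change.

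**What to change.** Replace the sentence in section 8 with:

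> *If the 200 mcg comparison is not significant, we will report the confidence interval at the level of the test and conclude only that reductions beyond its limit are ruled out (a 10 nmol, 20%, reduction if the interval excludes it). Smaller effects will not be regarded as excluded, and the result is inconclusive if the interval includes 10 nmol.*

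Two details should be settled at the same time. Hochberg can judge this comparison at 2.5% or 5%, so the interval level should be named. If the log-transform in section 13.2 is used, the 20% should be read as a ratio of geometric means.

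The cost is one sentence, carried into the SAP, and a narrower claim after a null result. The inconclusive branch will seldom be used if the planning assumptions hold: at 33 per arm it needs an estimate almost exactly at the boundary (4.995 to 5.005 nmol), and at 30 per arm one between 4.74 and 5.26. The main gain is that a null result is reported as ruling out an effect of about 20% and leaving smaller ones open. The inconclusive branch is a safeguard if precision is worse than planned; with a correlation of 0.5 and 30 per arm, it would cover estimates from 10 − 6.38 = 3.62 to 6.38 nmol.
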